### **Potential Benefits of the Proposed Research to Human Subjects and Others**

There may be no direct benefits to participating in the study. However, subjects in the intervention group may increase sleep duration and experience increased glucose control. The potential to future participants is that this study may advance the knowledge of sleep interventions to extend sleep duration and improve glucose control. The possible risks are no greater than those experienced in normal day-to-day life.

### **Importance of Knowledge to be Gained.**

The risks to the study participants are minimal and no more than those encountered in daily life. Knowledge gained from this study may provide an important intervention for improving sleep and glycemic control in the future in women with previous GDM. If effective, this intervention has important clinical implications for improving glycemic control and improving quality of life in this population. This intervention is scalable and could have public health impact.

## **8.0 Data Collection and Management Procedures**

Loss of confidentiality. Strict procedures will be put into place to minimize the risk of breach of confidentiality. All study staff will be trained on methods of maintaining subject confidentiality. Subjects will be assigned a unique code number. A master list that links the subject identity to the data will be kept by the principal investigator (PI) and stored in a locked office separately from the data. **Data storage:** All data will be stored and analyzed by code number. This consists of coded questionnaires, blood draw results, actigraphy. The coded data will be entered into a password-protected computer with a secure server for analysis, REDCap. Hard copy (paper copy) data (blood draw results) will be stored in a locked office. No identifiers (except subject ID) will be included. Only members of the research team will be able to access these data. **Procedures during data collection:** Privacy will be provided during recruitment by screening potential subjects in a private setting. The screening data that contain personal identifiers will be kept separate from the coded study data and stored in a locked office. All data collection and study procedures will take place in a private location. All data collected via the intervention (e.g. internet intervention materials, data entry, etc.) will be transmitted using Transport Layer Security (TLS) encryption to prevent eavesdropping and tampering information while it is in the transmission pipeline. To prevent unauthorized access to internet sites, they will be password protected.

Signed original informed consent documents and paper questionnaires will be stored in a locked cabinet in a locked room in the Division of Endocrinology and accessible only to the study PI. Access to the data will be determined by the PI and include study personnel at the level appropriate to complete their role in the study.

Samples will be stored as above described in [name] lab at -80degC. This lab is accessible only to approved endocrinology personnel with locked door access only.

Records (including the ICFs) will be maintained for at least 15 years following study completion.

## **9.0 Data Analysis**

- The data will be analyzed by the PI and team. Statistical assistance will be obtained from CCTS if needed.

## **10.0 Quality Control and Quality Assurance**

Activwatch data will be analyzed by a software provided by the manufacturer. Fitbit data will be automatically analyzed by the software of the manufacturer.

Data collected through the EMR will be obtained by study personnel and should a question of result validity be raised, the study PI will adjudicate entry or omission.

[name] and [name] will monitor the research and evaluate the data quality.

## **11.0 Data and Safety Monitoring**

- *Addresses how problems/side effects will be identified and handled.*
- *For studies that are minimal risk, describe how potential problems will be monitored and handled (e.g., breaches of confidentiality, emotional upset).*
- *For research involving more than minimal risk to subjects, describe:*
  - *Who will monitor adverse events (AEs) and unanticipated problems (UPs) involving risks to subjects or others and when events will be assessed.*
  - *How AEs or UPs will be recorded and communicated amongst research team members and who is responsible for making the reports.*
  - *The composition of the Data and Safety Monitoring Board (DSMB) and how frequently the DSMB meets, if one has been formed for the study.*
  - *Identify how often AEs and UPs will be monitored and what events will be reported to the sponsor and/or the IRB.*
  - *Describe stopping rules for the study.*
  - *Describe what occurs if a subject withdraws prematurely.*

### **Data Safety Monitoring Plan**

**CO PIs: [name], [name], [name]**

The risk associated with this study is minimal for the interventions and data collection methods employed by the study. The potential for a serious adverse event is very low. [name] will be the primary monitor, and a Safety Monitoring Committee will share the responsibility of monitoring the data.

The individuals responsible for data safety and monitoring will be [name], [name], [name] and [name], and a Study Monitoring Committee (SMC). A SMC will be appointed to provide oversight and monitoring of our data on an annual basis by individuals not directly associated with the study. The SMC will consist of: (1) [name] , PhD, RN, Assistant Professor, Department of Biobehavioral Health Science, College of Nursing; (2) [name], Professor of Medicine, Department of Medicine, Endocrinology, Diabetes and Metabolism; and (3) [name], RN, Assistant Professor, Department of Biobehavioral Health Science, College of Nursing; —all at UIC. Drs. [name], [name] and [name] have expertise in reviewing the scientific design, conduct of study, intervention fidelity, evaluation of safety and risks to subjects, interpretation of data, and making recommendations concerning continuation, modification, suspension, or termination of the study.

[name], [name], [name] and [name], will meet with the SMC annually and provide a written and verbal progress report. The report will include a summary of cumulative recruitment, randomization, cumulative retention and attrition rate, study group demographics, adverse events, and data completeness and quality. The SMC will provide oversight of the study, as well as consider factors external to the study that may impact the safety of the participants or the ethics of the study. A written report of the meeting will be compiled that summarizes the review of data and outcomes, as well as any recommendations with respect to modification of the protocol.

Subjects feeling uncomfortable with the procedures can choose to terminate their participation at anytime. Should this occur, the PI will record the events and share the information with the investigators.

The subjects will be compensated \$200 for completing the protocol, and they will be given a fit bit that is used during the protocol. If the baseline actigraphy revealed that their sleep duration is  $\geq 7$  hours during the work days or weekdays, they will receive \$30 but not be able to participate further. The control subjects will receive fitbit as well.

Potential breaches of confidentiality are guarded against by the above measures (section 8.0). However should personal information be mistakenly disseminated, action will be taken to secure study data, and study procedures for data safety and security will be re-evaluated. If necessary, subjects and the IRB will be notified according to Institutional policy.

## 12.0 Statistical Considerations

- *If a study incorporates qualitative rather than quantitative methods, indicate this and describe qualitative analysis and disregard the rest of this section.*
- Mean differences in glucose parameters between control and intervention groups will be analyzed using independent t-tests.
- Using a mean difference in fasting glucose values between women with a history of GDM who slept <6 hr vs ≥6 hr of 8 mg/dL, a total of 40 patients will have to be randomized to achieve power of 80% to detect a treatment difference at a two-sided 0.05 significance.
- For this pilot study, we will randomize at 2:1 sleep extension: control ratio.

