### **3.0 Objectives/Aims**

The specific aims are to determine:

**Aim 1:** Feasibility and acceptability of sleep extension intervention. Rationale: Analysis of recruitment, retention and participant program evaluation will provide feasibility and acceptability data. Hypothesis: Sleep extension intervention will be feasible and acceptable to the target population. Approach: Feasibility will be determined through analysis of recruitment and retention. Acceptability will be determined through participant evaluation.

**Aim 2:** Efficacy of sleep extension intervention on primary outcomes of glucose metabolism. Rationale: Short sleep duration was associated with abnormal glucose metabolism in women with previous GDM. Sleep optimization in short sleeping individuals without diabetes resulted in improved insulin resistance. Hypothesis: Sleep extension intervention will result in improved glycemic control. Approach: A randomized controlled trial of an 8-week sleep extension intervention compared to a healthy living information control group on glucose metabolism as measured by an oral glucose tolerance test and A1C at baseline and at the end of intervention.

**Aim 3:** Efficacy of sleep extension intervention on secondary outcomes of weight, appetite regulating hormones, energy expenditure, inflammatory markers, depressive symptoms and subjective sleep quality.

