### **4.0 Eligibility**

We will recruit 60 subjects for this study

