### **Study protocol**

#### **1. Baseline assessment:**

- One week of actigraphy will be recorded using an actiwatch spectrum. If during this assessment it is found that their sleep duration is  $\geq 7$  hours during the weekdays or work days, they will not be able to participate further.
- Subjects will answer sleep, physical activity, depression questionnaires, quality of life, anxiety symptoms and perceived stress symptoms.
- Weight, height, waist and hip circumference, and neck circumference will be obtained
- Eating behaviors, appetite and 24 hour food recall will be obtained through questionnaires.
- 
- At the end of one week, they will return to have a 75-gram oral glucose tolerance test (OGTT) done at the clinical research center (see below procedure).

- Blood will be assayed for A1C, serum creatinine, lipid panel and CBC.
- Blood will be saved for assay for genetic analysis, appetite regulating hormones (leptin, ghrelin, PYY, 2-arachidonoylglycerol (2-AG)), and inflammatory markers (CRP, IL-1, IL-6), and metabolomics profiles.
- Stool sample will be collected for stool microbiome assay
- Resting metabolic rate will be performed
- Additional serum samples will be stored for future analysis

2. The subjects will then be randomized to healthy living control group or sleep extension group for 6 weeks (see blow detail).
3. At week 6, they will be given an actiwatch to wear for one week. At week 7, the following procedures will take place
  - They will return to the CRC to have a repeated 75-gram OGTT done.
  - Weight will be obtained
  - Subjects will answer sleep, depression questionnaires, quality of life, anxiety symptoms and perceived stress symptoms.
  - Eating behaviors, appetite and 24 hour food recall will be obtained through questionnaires.
  - Blood will be assayed for A1C, lipid panel.
  - Blood will be saved for later assay for appetite regulating hormones (leptin, ghrelin, PYY, 2-arachidonoylglycerol (2-AG)), and inflammatory markers (CRP, IL-1, IL-6) and metabolomics profiles.
  - Stool sample will be collected for stool microbiome assay
  - Resting metabolic rate will be performed
  - Additional serum samples will be stored for future analysis
  - Participant evaluation of the program will be obtained through questionnaires and interview.
4. At week 10, subject will be given an actiwatch for one week. And,
  - They will return to the CRC to have fasting glucose and insulin level done.
  - Weight will be obtained

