**3. Oral Glucose Tolerance Test (OGTT).** After an overnight fast, the subject will arrive at the CRC between 8-9 am. Blood samples will be obtained at 0 minutes for glucose and insulin. Then 75 grams glucose solution will be given orally. Blood samples will be obtained at 30, 60, 90, 120 minutes for glucose and insulin. Extra blood samples will also be obtained at 0 minutes and stored for further analysis. **Total blood volume 60 ml per one OGTT visit.**

**4. Blood samples** will be obtained for lipid panel, creatinine and A1C at baseline and at week 6. CBC will be obtained at baseline. Fasting glucose and insulin will be obtained at week 10. Blood will be saved for later assay for genetic analysis, appetite regulating hormones (leptin, ghrelin, PYY, 2-arachidonoylglycerol (2-AG)), and inflammatory markers (CRP, IL-1, IL-6) and metabolomics profiles. **Total blood sample 20 ml at each visit.**

**5. Microbiome** Stool samples to measure the gut microbiome will be collected at week 0 and week 6. Changes in sleep may alter the gut microbiome and potentially influence glycemia. Participants will be provided a collection device (Easysampler®, ALPCO, Inc.) and return the specimen at a subsequent visit. Remaining stool samples will be stored in a freezer at the College of Medicine for later analysis by UIC researchers.

**6. Resting energy expenditure:** Oxygen consumption will be measured through indirect calorimetry using the Vyntus CPX system metabolic cart (Vyaire Medical, Mettawa, IL). In this test, a canopy hood is placed over the subject's head as he/she reclines in bed. One end of the canopy has tubing connected to the metabolic cart, while the other end of the canopy is open to room air. During the 30-40 minute procedure, expired gases are measured and resting energy expenditure is calculated using the Harris-Benedict equations. This will be performed during fasting.

**7. Feasibility and acceptability of Sleep extension:** Feasibility will be determined through analysis of recruitment (number recruited, screened, eligible, and consented) and retention (% session participation, program completion rates). Acceptability will be determined through participant evaluation (written evaluation and interview at program completion). See Appendix B.

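### Glucose outcomes all have a pre-randomization value, but only unadjusted t-tests are planned; ANCOVA on baseline would be more precise using data already collected

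*Combined protocol and SAP*

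**What the plan says.** Section 12.0 (Statistical Considerations) of the combined protocol and SAP states: "Mean differences in glucose parameters between control and intervention groups will be analyzed using independent t-tests". Section 9.0 (Data Analysis) adds no method. Baseline adjustment is not mentioned anywhere, and the text does not say whether the t-test is run on follow-up values or on changes.

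Baseline values exist for every glucose outcome:

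- Aim 2 in Section 3.0 defines glucose metabolism "as measured by an oral glucose tolerance test and A1C at baseline and at the end of intervention".
- In Section 6.0, at the end of the baseline week "they will return to have a 75-gram oral glucose tolerance test (OGTT) done at the clinical research center", with glucose and insulin sampled at 0, 30, 60, 90 and 120 minutes. A1C is also assayed at baseline.
- Randomization is the next step: "The subjects will then be randomized to healthy living control group or sleep extension group for 6 weeks".
- The OGTT and A1C are repeated at week 6–7. Later, "Fasting glucose and insulin will be obtained at week 10"; the 0-minute sample of the baseline OGTT is the matching baseline value.

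On size, Section 4.0 says "We will recruit 60 subjects for this study". Section 12.0 says that, for a fasting glucose difference of 8 mg/dL, "a total of 40 patients will have to be randomized to achieve power of 80% to detect a treatment difference" at two-sided 0.05, and adds: "For this pilot study, we will randomize at 2:1 sleep extension: control ratio".

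**The concern.** A t-test on follow-up values ignores what the baseline measurement already explains about each woman's glucose. A t-test on changes uses the baseline but fixes its coefficient at 1, which adds noise when the correlation is low. ANCOVA estimates the coefficient, so it is more precise than either test at any plausible correlation.

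This matters more than usual here because 60 women at 2:1 leaves about 20 controls. The 8 mg/dL planning effect is an observational contrast between shorter and longer sleepers, and the effect of the intervention may be smaller. Leaving the t-test undefined also allows the choice between final values and changes to be made after the data are seen.

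**Working it through.** **Inputs from the documents.** Effect 8 mg/dL, two-sided α 0.05, power 80% at N = 40, 2:1 allocation (Section 12.0); 60 women (Section 4.0), so 40:20.

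**Assumptions.** The documents give no SD and no r. I take r from 0.3 to 0.8 and obtain the SD by inverting the plan's own calculation. I assume equal SDs at baseline and follow-up and in both arms.

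**The plan's figure.** N = 40 cannot be reproduced without an SD; it can only be inverted. A noncentral-t calculation gives 80% power with 38 df when effect/SE is about 2.88.

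- 1:1 (20:20): SD = 8 / (2.875 × √(1/20 + 1/20)) = 8.80 mg/dL.
- 2:1 (27:13): SD = 8 / (2.876 × √(1/27 + 1/13)) = 8.24 mg/dL.

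**Variance relative to a final-value t-test.**

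- ANCOVA: 1 − r².
- Change scores: 2(1 − r), which exceeds 1 when r is below 0.5.
- ANCOVA relative to change scores: (1 − r²) / [2(1 − r)] = (1 + r)/2.

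**Results at 40:20, SD 8.8.** The SE of a final-value comparison is 8.8 × √(1/40 + 1/20) = 2.41 mg/dL. Degrees of freedom are 58 for the t-tests and 57 for ANCOVA. The final-value t-test does not depend on r: its 95% CI half-width is 4.8 mg/dL, its detectable difference at 80% power is 6.87 mg/dL, and its power is 90% at 8 mg/dL and 37% at 4 mg/dL (4 mg/dL is illustrative).

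| | r = 0.3 | r = 0.5 | r = 0.7 | r = 0.8 |
|---|---|---|---|---|
| ANCOVA: variance ratio 1 − r² | 0.91 | 0.75 | 0.51 | 0.36 |
| ANCOVA: CI half-width, mg/dL | 4.6 | 4.2 | 3.5 | 2.9 |
| ANCOVA: detectable difference, mg/dL | 6.55 | 5.95 | 4.90 | 4.12 |
| Change scores: detectable difference, mg/dL | 8.12 | 6.87 | 5.32 | 4.34 |
| ANCOVA: power at 8 mg/dL | 93% | 96% | >99% | >99% |
| Change scores: power at 8 mg/dL | 79% | 90% | 99% | >99% |
| ANCOVA: power at 4 mg/dL | 40% | 47% | 63% | 78% |
| Change scores: power at 4 mg/dL | 28% | 37% | 56% | 73% |

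At r = 0.5, a final-value t-test would need about 60/0.75 = 80 women to match ANCOVA with 60.

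**Cost of estimating the slope.** The table leaves out an average variance inflation of 1 + 1/(N − 4), which is 1.018 at N = 60 and 1.028 at N = 40. With it, ANCOVA power at 40:20, SD 8.8 and 8 mg/dL is 92.4% at r = 0.3 and 96.2% at r = 0.5. A simulation with the slope estimated (20,000 replicates, r = 0.5) gives 90.2% for the final-value t-test, 90.6% for changes and 96.3% for ANCOVA. ANCOVA overtakes the final-value test once r exceeds about √(1/57) = 0.13 at N = 60, or √(1/37) = 0.16 at N = 40. It beats change scores for any r below about 0.95.

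**If only 40 women (27:13) give data, 8 mg/dL, slope inflation included.**

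- SD 8.8: final-value t-test 74.7%; ANCOVA 77.4% (r = 0.3) or 84.8% (r = 0.5); change scores 60.2% or 74.7%.
- SD 8.24: final-value t-test 80.0%; ANCOVA 82.5% or 89.1%; change scores 65.9% or 80.0%.

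**Type I error.** At 40:20, r = 0.6 and equal SDs (40,000 replicates), ANCOVA gives 5.05% with model-based standard errors, 6.0% with HC0 and 4.7% with HC3.

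**The case against.** The t-test is unbiased and valid, the trial calls itself a pilot, and Aim 1 is feasibility. At the plan's own 8 mg/dL with all 60 women, a final-value t-test already has about 90% power (SD 8.8) or 94% (SD 8.24), and ANCOVA at r = 0.3 to 0.5 adds only about 2 to 6 points. Larger gains need a smaller effect, fewer completers or a higher r, and the documents give none of these. The wording of Section 12.0, and its sample-size sentence about fasting glucose values, lean towards final values, so the poor change-score figures may never apply. Nor is ANCOVA strictly free: it spends one degree of freedom and about 2–3% of variance.

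Most of this stands, and it limits the size of the point. The change-score column should not carry the argument; it shows only why the choice needs stating. The cost of ANCOVA is real but small: even at r = 0, power at 8 mg/dL falls only from 90.4% to 89.9% at N = 60 (SD 8.8), and from 80.0% to 78.9% at N = 40 (SD 8.24). Pilot status does not remove the point, because Aim 2 calls the glucose measures primary outcomes, Section 12.0 gives a power calculation for them, and a narrower interval also helps in planning a later trial.

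**Conclusion.** The point holds as an efficiency weakness that should be corrected; the planned test is not invalid. At r between 0.3 and 0.7, ANCOVA removes 9% to 49% of the variance of a final-value t-test and shortens the 95% CI half-width for fasting glucose from 4.8 to between 4.6 and 3.5 mg/dL (40:20, SD 8.8). The power gain is modest at 8 mg/dL with complete data. It is larger if the true effect is smaller, if fewer women give data, or if the t-test is run on changes and r is low. The direction needs only r above about 0.13 to 0.16. The size depends on an SD and an r that the documents do not state, and the mg/dL figures apply to fasting glucose only.

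**What to change.** Replace the t-test sentence in Section 12.0 with wording such as:

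> Each week 6–7 glucose parameter (A1C, OGTT glucose and insulin), and week-10 fasting glucose and insulin, will be compared between arms by ANCOVA with randomized arm and the baseline value of the same parameter as covariates. The adjusted difference will be reported with its 95% CI.

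Three details should go with it:

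- The Protocol Overview shows A1C at both screening and week 0–1. State that the week 0–1 value is the covariate.
- If robust standard errors are used, specify HC3; with about 20 controls, HC0 is too liberal.
- If an unadjusted comparison is also shown, say whether it uses final values or changes, and use the Welch form.

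The cost is a few lines of analysis text. No extra data, visits or participants are needed.

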diabetes who had habitual short sleep duration led to improved fasting insulin resistance. (4) A pilot trial of our newly developed technology-assisted behavioral sleep optimization intervention in individuals with short sleep duration demonstrated a clinically significant sleep duration increase (median 35 minutes). **Therefore, this proposal seeks to improve glucose metabolism in women with a prior history of GDM and habitual short sleep using sleep extension intervention under a randomized controlled design.**

Our novel technology-assisted sleep intervention was developed to leverage a rapidly increasing public interest in sleep tracking, especially wearable sleep tracker use by consumers (+500% in 3 years). Our technology employs four elements -- a wearable sleep tracker, didactic content, an interactive smartphone application and brief telephone counseling . This study will randomize 60 non-diabetic women with a history GDM who report short sleep duration to an eight-week sleep extension intervention group or a healthy living information control group. We hypothesize that this sleep extension intervention will be feasible, acceptable and improve glucose metabolism.

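### Section 12 asks for 40 women randomized for 80% power, while other sections randomize 60 or recruit 60; the numbers are not reconciled, and no power is stated for 60 at 2:1

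*Combined protocol and SAP*

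**What the plan says.** Section 12.0 plans independent t-tests of the glucose parameters. It then takes a fasting-glucose contrast between women with prior GDM "who slept <6 hr vs ≥6 hr of 8 mg/dL" and states that "a total of 40 patients will have to be randomized to achieve power of 80% to detect a treatment difference" at a two-sided 0.05 level. No SD for fasting glucose and no expected loss appear there or anywhere else in the document.

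The next bullet reads: "For this pilot study, we will randomize at 2:1 sleep extension: control ratio". It does not say whether the 40 was computed at that ratio.

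Two other sections give a different number. Section 2.0: "This study will randomize 60 non-diabetic women with a history GDM". Section 4.0: "We will recruit 60 subjects for this study".

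Section 6.0 places A1C and pregnancy testing after consent. It then places a week of actigraphy before randomization, and women who sleep 7 hours or more on work days or weekdays go no further. The Data Safety Monitoring Plan in Section 11.0 sets a separate payment for women removed at the actigraphy step. No expected rate is given for either step.

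**The concern.** The protocol gives two numbers to be randomized (40 and 60) and one number to be recruited (60), with nothing to connect them. Because some women leave between consent and randomization, 60 recruited and 60 randomized need not be the same trial. The 80% belongs to the 40, and no power or detectable difference is given for 60 at 2:1.

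Aim 2 makes glucose metabolism the primary efficacy outcome, so the power statement carries weight even in a pilot. As written, it cannot be checked. It does not tell study staff whether enrolment ends at 40 randomized, 60 randomized or 60 consented, and it does not tell a reader what difference the trial was designed to detect.

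The point concerns the SD, allocation, loss and target number. It does not depend on whether 8 mg/dL is a sensible treatment effect.

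**Working it through.** **Inputs from Section 12.0:** difference 8 mg/dL; two-sided alpha 0.05; power 80%; total 40; two-sample t-test; allocation 2:1 (next bullet). **From Sections 2.0 and 4.0:** 60 randomized, 60 recruited. **Not in the documents, so assumed:** the SD (back-solved from the 40) and all loss and exclusion rates.

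**Formula.** Power is taken from the noncentral t distribution with n1 + n2 − 2 degrees of freedom and noncentrality (8/SD) / √(1/n1 + 1/n2).

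**Step 1: can the 40 be reproduced?** Not forward, because there is no SD. Solving for the SD that makes 40 give 80%:

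- At 1:1 (20:20): SD 8.80, a standardized difference of 8/8.80 = 0.909. The normal approximation at SD 9 gives n per arm = 2 × (9 × 2.8016/8)² = 19.9, so 20 per arm and 40 in total.
- At 2:1: SD 8.24 for 27:13, 8.39 for 26:14, and 8.30 for an exact 2:1 split.

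Both bases give 40 with an SD between 8 and 9, so the text does not show which was used.

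**Step 2: power for 8 mg/dL under each basis.**

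| Women analysed | SD 8.8 (if 40 was 1:1) | SD 8.3 (if 40 was 2:1) |
|---|---|---|
| 40 at 2:1, no loss | 75% (27:13) | 80% (exact 2:1) |
| 36 (24:12): 40 randomized, assumed 10% loss | 71% | 75% |
| 45 (30:15) | 80% | 85% |
| 60 (40:20), no loss | 90% | 93% |
| 51 (34:17): 60 randomized, assumed 15% loss | 85% | 89% |
| About 41: 60 recruited, assumed 20% post-consent failure and 15% loss | 76% | 81% |

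The last row is 60 × 0.80 × 0.85 = 40.8 analysed, split 2:1.

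**Step 3: how much loss 60 randomized can absorb.** At 40:20, power stays at or above 80% up to about 25% loss at SD 8.8, where 45 remain. At SD 8.3 it does so up to about one third, where 40 remain.

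**Step 4: what can be stated without knowing the SD.** The difference detectable with 80% power is 0.78 SD for 40:20 and 0.85 SD for 34:17. At SD 8.8 these are 0.78 × 8.8 = 6.9 mg/dL and 0.85 × 8.8 = 7.5 mg/dL.

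**Step 5: dependence on the SD.** If the SD is larger than the 40 implies, power falls. With 60 at 2:1 and no loss it is 89% at SD 9, 82% at SD 10 and 67% at SD 12. The largest SD that keeps 80% is about 10.3 with no loss and 9.1 with 20% loss.

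**The case against.** The strongest reply is that nothing here is shown to be wrong. The 40 can be read as a minimum, and randomizing 60 exceeds it by half. The 2:1 ratio stands directly after the power sentence, so the 40 may already be a 2:1 figure. For every two-sided SD that makes 40 correct, 60 randomized at 2:1 has more than 80% power. The word recruit in Section 4.0 may be loose usage for randomize. The study calls itself a pilot with feasibility as its first aim, and what a null result excludes will be read from the confidence interval rather than from planned power.

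Most of this stands, and it rules out two stronger readings. A reader might infer that the 40 is an arithmetic error, a 1:1 figure wrongly carried into a 2:1 trial. The documents do not support that, because without an SD the 1:1 basis is only one of two that fit. A reader might also infer that the trial is underpowered. For 60 randomized and an SD near those implied by the 40, the reverse is true. The shortfall under 60 recruited rests on assumed exclusion and loss rates, and at SD 8.3 the same scenario still gives about 81%.

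The reply does not remove the conflict in numbers. Reading 40 as a minimum is an inference, since nothing presents 60 as an inflation of 40 for loss, exclusions or unequal allocation. The pilot label does not help either, because Section 12.0 still makes a power claim for an efficacy comparison.

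**Conclusion.** The point holds as an unreconciled and uncheckable sizing statement. Sections 2.0, 4.0 and 12.0 give numbers that are not connected, and the 40/80% sentence does not describe a trial of 60 at 2:1.

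The size of the problem depends on which number is followed. With 40 randomized at 2:1, power for 8 mg/dL is about 75% if the 40 was a 1:1 figure (45 would be needed). It is 80% if the 40 was a 2:1 figure, and then only with no loss. With 60 randomized, the plan is adequate for 8 mg/dL on either basis. With 60 recruited, power may fall on either side of 80%.

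These figures rest on SDs back-solved from the 40 and, where marked, on assumed loss and exclusion rates. If the true SD is above about 10, even 60 at 2:1 would fall short of 80% for 8 mg/dL once some women are lost. The point should be corrected, but it does not put the trial's design in doubt.

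**What to change.** Reconcile Sections 2.0, 4.0 and 12.0 to one number randomized, and say separately how many women are expected to consent in order to reach it. Replace the 40/80% sentence with a statement for that number at 2:1. For 60 randomized it could read: 60 women randomized 40:20; two-sided 5% t-test; 80% power to detect 0.78 SD, or 0.85 SD if 15% lack the week-7 value; SD and its source stated, with the difference in mg/dL. The 15% is a placeholder for the sponsor's own expected loss.

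If 60 randomized is already the working plan, the cost is protocol wording and a changed power figure. If 60 meant consented, reaching 60 randomized takes more consents, with the extra A1C tests and actigraphy weeks: 60/0.80 = 75 at an assumed 20% post-consent failure, or 60/0.70 ≈ 86 at 30%. In that case the sponsor can keep 60 consented, say so in Section 2.0, and restate the power or detectable difference for the number it expects to randomize.
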